### 8.6.2.1 Definition of Dose-Limiting Toxicities

All toxicities will be graded using National Cancer Institute (NCI) CTCAE Version 4.0 (Appendix 12.7).

The occurrence of any of the following toxicities during Cycle 1 will be considered a DLT, if judged by the Investigator to be possibly, probably or definitely related to study treatments.

1. Grade 4 hematologic toxicity lasting  $\geq 14$  days.
2. Grade 4 non-hematologic toxicity (not laboratory).
3. Grade 3 non-hematologic toxicity (not laboratory) lasting  $> 3$  days despite optimal supportive care except inadequately treated hypersensitivity reactions
4. Any Grade 3 or higher non-hematologic laboratory value if:
  - Medical intervention is required to treat the subject, or
  - The abnormality leads to hospitalization, or
  - The abnormality persists for  $> 1$  week.
5. Febrile neutropenia Grade 3 or Grade 4:
  - Grade 3 is defined as ANC  $< 1000/\text{mm}^3$  with a single temperature of  $> 38.3$  degrees C (101 degrees F) or a sustained temperature of  $\geq 38$  degrees C (100.4 degrees F) for more than one hour.
  - Grade 4 is defined as ANC  $< 1000/\text{mm}^3$  with a single temperature of  $> 38.3$  degrees C (101 degrees F) or a sustained temperature of  $\geq 38$  degrees C (100.4 degrees F) for more than one hour.

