Abbreviations: AEs = adverse events; AFP = alpha fetoprotein; APRI = aspartate aminotransferase:platelet ratio index; aPTT = activated partial thromboplastin time; BP = blood pressure; CBC = complete blood count; DC = discontinuation; ECG = electrocardiogram; ECOG = Eastern Cooperative Oncology Group; FT4 = free thyroxine; HBV = hepatitis B virus; HBcAg = hepatitis B core antigen; HBsAb = anti-HBsAg antibody; HBsAg = hepatitis B surface antigen; HCV = hepatitis C virus; ICF = informed consent form; IGF-1 = insulin-like growth factor-1; INR = international normalized ratio; P = pulse; Q3W = every 3 weeks; Q9W = every 9 weeks; Q12W = every 12 weeks; RR = respiratory rate; T = temperature; PT = prothrombin time; T3 = triiodothyronine; TSH = thyroid-stimulating hormone.

- In subjects that experience site-assessed PD or start a new anti-cancer therapy, contact should be made (eg; by telephone) Q12W to assess for survival status.
- Cycle 1 treatment must be given within 3 days of allocation. The window for each visit is ±3 days until the end of treatment and ±7 days during follow-up.
- Height will be measured at screening only. For women of reproductive potential, a urine or serum pregnancy test should be performed within 72 hours prior to Day 1 of each treatment cycle and 30 days post treatment.
- A serum test can be done if urine is not appropriate. Additionally, if urine test is positive or is not evaluable, a serum test is required. Subjects must be excluded/discontinued in the event of a positive test results Monthly pregnancy testing should be conducted as per local regulations where applicable.
- ECOG Performance Status and laboratory tests for screening and determining eligibility are to be performed within 7 days and 10 days, respectively, prior to the first dose of trial treatment.
- CBC with differential and chemistry to be performed every cycle
- Liver panel (albumin, ALT, AST, total and direct bilirubin, and alkaline phosphatase) to be performed at screening and then every week for the first 2 cycles followed by every cycle starting at cycle 3. Liver panel will also be done at discontinuation and safety follow-up.

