## 8.6.2 Statistical Methods for Safety Analyses

Safety and tolerability will be assessed by clinical review of all relevant parameters including AEs, laboratory tests, and vital signs.

Counts and percentages of subjects with AEs will be provided. Analysis of AEs will be descriptive.

Bayesian toxicity monitoring will be performed to ensure that treatment is safe. Dose-limiting toxicity (DLT) is defined as Grade 3 or higher non-hematologic toxicity or Grade 4 or higher hematologic toxicity as per below. DLTs will be assessed during the first cycle of combination therapy. A DLT rate of 30% or higher is considered excessive. We will hold the patient enrollment if the probability of excessive toxicity is high (i.e.,  $\text{Prob}(\text{DLT} > 0.3) > 0.8$ ). This corresponds to withhold new patient entry when 3 DLTs are observed in 5 to 6 patients, 4 DLTs in 7 to 9 patients, 5 DLTs in 10 to 12 patients, or 6 DLTs in 13 to 14 patients, respectively. The probability of withholding new patients upon entry (early stopping) is 0.02, 0.15, 0.41, 0.68, and 0.88 if the true DLT rates are 0.1, 0.2, 0.3, 0.4, and 0.5, respectively. The calculation assumes that the prior distribution of the probability of DLT is beta(0.5, 0.5).

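### For blood counts and non-hepatic chemistry, the Cycle 1 laboratory schedule cannot establish the durations that DLT items 1 and 4 require, so the Bayesian hold rule can undercount

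*Combined protocol and SAP*

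**What the plan says.** Section 8.6.2 sets the observation window: "DLTs will be assessed during the first cycle of combination therapy". Section 8.6.2.1 opens its list with "The occurrence of any of the following toxicities during Cycle 1 will be considered a DLT", subject to attribution to treatment. A cycle is three weeks (Table 3).

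Two entries depend on duration:
- Item 1 is "Grade 4 hematologic toxicity lasting" 14 days or more.
- Item 4 covers Grade 3 or higher non-hematologic laboratory values. It has three alternative limbs: treatment ("Medical intervention is required to treat the subject, or"), hospitalization, and "The abnormality persists for" more than one week.

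In the flow chart (section 6.1), the CBC and chemistry rows are marked at screening, blank at Cycle 1 and marked from Cycle 2. Footnote f adds only "CBC with differential and chemistry to be performed every cycle". The liver panel row has the same blank at Cycle 1, but footnote g requires that panel "to be performed at screening and then every week for the first 2 cycles".

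Section 7.1.3.1 allows pre-dose samples up to 72 hours before dosing after Cycle 1. It requires results to be acceptable before each dose, and drug-related abnormal values to be followed until they resolve. For ribavirin-treated subjects it recommends hematology, including hemoglobin, at Weeks 2 and 4.

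**The concern.** A duration needs at least two dated measurements. For blood counts and for chemistry outside the liver panel (creatinine, electrolytes, glucose), the schedule supplies one after the first dose. An abnormality that meets the definition can therefore go unseen, or be seen without a datable start.

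The protocol foresees toxicities of this kind. Section 5.2.1.2 says immune-related events may appear shortly after the first dose, and Table 6 includes hyperglycemia and renal dysfunction. Section 5.2.1.5 places ribavirin anemia within one to two weeks of starting and warns of severe falls in neutrophils and platelets.

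Tolerability is a primary objective in both arms (section 3.1). The Bayesian rule in section 8.6.2 is the plan's only numerical safety stop, and its stated hold probabilities assume that every DLT is observed. One DLT can decide a boundary: three in six holds enrolment and two in six does not.

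**Working it through.** **1. Reproduce the plan's figures.** Inputs, all from section 8.6.2: prior beta(0.5, 0.5), hold if Pr(DLT rate > 0.3) > 0.8, and boundaries of 3 DLTs in 5–6 patients, 4 in 7–9, 5 in 10–12 and 6 in 13–14. Section 8.9 gives 15 subjects per arm.

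The posterior after x DLTs in n patients is Beta(0.5 + x, 0.5 + n − x). For example, 3 in 6 gives 0.857 (hold) and 3 in 7 gives 0.778 (no hold); 5 in 12 gives 0.814 (hold) and 5 in 13 gives 0.754 (no hold). All listed boundaries agree.

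The hold probability comes from the exact recursion P(n, x) = P(n−1, x)(1 − p) + P(n−1, x−1)p, removing the mass at or above the boundary after each patient from n = 5 to 14.

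| True DLT rate | 0.1 | 0.2 | 0.3 | 0.4 | 0.5 |
|---|---|---|---|---|---|
| Stated | 0.02 | 0.15 | 0.41 | 0.68 | 0.88 |
| Recomputed | 0.020 | 0.147 | 0.398 | 0.676 | 0.875 |

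The plan's arithmetic is sound.

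**2. Set the definition against the schedule.** Cycle 2 Day 1 is nominally Day 22. A sample 72 hours ahead of an on-time dose falls on Day 19, and the ±3-day visit window extends to Day 25. In every case it is one sample.

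- *Item 1, CBC:* one post-dose value shows no duration. With ribavirin, Week 2 (about Day 15) to the Cycle 2 sample spans 22 − 15 = 7 days, short of 14.
- *Item 4, liver tests:* weekly values at about Days 8, 15 and 22 span 22 − 8 = 14 days, so persistence beyond one week can be shown.
- *Item 4, other chemistry:* one post-dose value, so the persistence limb cannot be shown.

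**3. What can be missed.**
- A non-hepatic chemistry abnormality lasting just over 7 days can start as late as about Day 14 and resolve before Day 22 without being sampled.
- A Grade 4 cytopenia lasting 14 days escapes the Cycle 2 sample only if it starts by about Day 22 − 14 = Day 8. A later one is still present on Day 22, but its start is unknown. For illustration, one running from Day 12 to Day 27 lasts 15 days and qualifies; from first detection, it shows 27 − 22 = 5 days.

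**4. Effect on the hold rule.** If m is the absolute DLT rate that goes unseen, the rule operates at p − m. The documents give no value for m, so the values below are assumptions.

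| m | Rate seen when p = 0.40 | Hold probability, p = 0.40 | Hold probability, p = 0.50 |
|---|---|---|---|
| 0 | 0.40 | 0.676 | 0.875 |
| 0.02 | 0.38 | 0.624 | 0.844 |
| 0.05 | 0.35 | 0.541 | 0.789 |
| 0.10 | 0.30 | 0.398 | 0.676 |

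**The case against.** The strongest reply is that little would be lost in practice. Several parts of it stand:

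- The liver panel is chemistry (Table 10 lists its analytes there) and is weekly under footnote g. It covers the laboratory values that the protocol tracks as hepatic events of clinical interest.
- Two of item 4's three limbs need no duration. Item 9 counts a toxicity-related delay of more than a week in starting Cycle 2, and item 10 counts failure to complete 80% of treatment. Items 5 and 6 count febrile neutropenia and severe thrombocytopenia with bleeding.
- Most Grade 4 cytopenias lasting 14 days would still be present at the Cycle 2 sample and would then be followed to resolution. Section 7.1 also allows unscheduled tests.
- Section 8.6.2.1 requires occurrence in Cycle 1. It does not say that the duration must end by Day 21, and item 9 can only be judged after that.

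These points narrow the gap without closing it. Follow-up starts only once an abnormality has been detected, unscheduled tests need a clinical prompt, and item 9 does not catch a value that has recovered by Cycle 2. Whether later days count is unstated, and it matters: for a ribavirin subject, Week 2 to Week 4 spans 14 days, so the answer decides whether hematology at those two points can meet item 1.

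A reader might infer that no laboratory test at all falls between dose 1 and Cycle 2, or that duration-based laboratory DLTs can contribute nothing to the count. The documents support neither, because of the weekly liver panel, the recommended ribavirin hematology and the follow-up rule.

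**Conclusion.** The point holds for CBC and non-hepatic chemistry only. Scheduled Cycle 1 data cannot establish the 14-day condition of item 1, or item 4's one-week condition for analytes outside the liver panel. The clearest losses are a non-hepatic Grade 3 or higher chemistry abnormality that lasts more than a week and resolves untreated before Cycle 2, and a cytopenia whose onset cannot be dated.

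Any such loss lowers the DLT count, but its size cannot be derived from the documents. With 2, 5 or 10 points of a true 0.40 rate unseen, the hold probability is about 0.62, 0.54 or 0.40 instead of 0.68. The upper figure would require a quarter of all DLTs (0.10/0.40) to be of this type and undetected, and nothing in the documents supports that. The table shows sensitivity and is not an estimate.

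Two further readings go too far. The stopping probabilities are not miscalculated; they assume complete observation of DLTs. Nor is the Bayesian rule the only safeguard: section 5.9 allows termination on risk/benefit, and section 7.2.4.3 has the investigator monitor aggregated safety data. It is the only numerical rule, which is why a complete count is worth securing at low cost.

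**What to change.** 1. Reconcile the duration conditions in section 8.6.2.1 with the Cycle 1 laboratory schedule. One way is to add CBC and chemistry to the weekly draws that footnote g already requires in Cycle 1.
2. Reconcile the liver panel row, blank at Cycle 1, with its weekly footnote. The first change relies on those draws taking place.
3. State in section 8.6.2.1 whether a toxicity with onset in Cycle 1 counts when its duration is completed after Day 21, and how onset is dated when the first abnormal value is the Cycle 2 sample.

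The cost is extra tubes at existing draws for one cycle, one flow-chart edit and a sentence or two in the DLT section. If footnote g is followed as written, no visits are added. The boundaries, prior and sample size do not change.

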# Proprietary Information of MD Anderson

Protocol # 2016-0251

Date: February 24, 2020

116

degrees F) for more than one hour, with life-threatening consequences and urgent intervention indicated.

6. Thrombocytopenia <25,000/mm^3 if associated with:
  - A bleeding event which does not result in hemodynamic instability but requires an elective platelet transfusion, or
  - A life-threatening bleeding event which results in urgent intervention and admission to an Intensive Care Unit.
7. Grade 5 toxicity (i.e., death).
8. Delay in the scheduled administration of any component of therapy (IPI, PEG-INF, MK-3475) of >14 days
9. A delay of > 1 week due to drug-related toxicity in initiating Cycle 2.
10. Unable to complete at least 80% of any of the three treatments during the first course of therapy due treatment-related toxicity (even if not meeting above DLT criteria).

## 8.6.3 Demographic and Baseline Characteristics

The number and percentage of subjects screened, allocated, the primary reasons for screening failure, and the primary reasons for discontinuation will be displayed. Demographic variables (e.g., age, gender), baseline characteristics, primary and secondary diagnoses, and prior and concomitant therapies will be summarized either by descriptive statistics or categorical tables for all enrolled subjects.

## 8.7 Interim Analyses

No Interim analysis planned. Analysis of DLTS will be performed continuously as subjects are enrolled.

## 8.8 Multiplicity

No multiplicity adjustment is planned in this study.

## 8.9 Sample Size

In this study, approximately 15 subjects will be enrolled per Arm.

## 8.10 Subgroup Analyses and Effect of Baseline Factors

No subgroup analysis planned.

## 8.11 Compliance (Medication Adherence)

Drug accountability data for pembrolizumab will be collected during the study. Any deviation from protocol-directed administration will be reported.

## 8.12 Extent of Exposure

Extent of Exposure for a subject is defined as number of cycles in which the subject receives the study medication infusion. Summary statistics will be provided on Extent of Exposure for the ASaT population.

## 8.13 Statistical Analysis of HCV Endpoints

### 8.13.1 HCV endpoints

#### 1. Primary endpoint

**Objective:** To evaluate the efficacy of pembrolizumab in combination with Zepatier as assessed by the proportion of subjects with HCV GT1 or GT4 achieving Sustained Virologic Response 12 weeks after the end of all HCV study therapy (SVR12), defined as HCV RNA below the lower limit of quantitation (LLOQ) (either target detected unquantifiable [TD(u)] or target not detected [TND]) 12 weeks after the end of all study therapy.

#### 2. Secondary endpoint

(4) **Objective:** To evaluate the safety of pembrolizumab in combination with Zepatier as assessed by the proportion of subjects with HCV GT1 or GT4 achieving SVR12 and SVR24, defined as HCV RNA below the LLOQ (either TD[u] or TND) 12 and 24 weeks after the end of all study therapy.

#### 3. Exploratory endpoints

The proportion of subjects achieving undetectable HCV RNA (TND) and HCV RNA <LLOQ (TD[u]) at Week 2, Week 4, and Week 12 or Week 16 (for those treated for 16 weeks), and the proportion of subjects achieving SVR4 in the immediate treatment arm.

- (1) **Objective:** To assess whether pembrolizumab in combination with Zepatier affects the course of viral infections in subjects with underlying HCV GT1 or GT4. We hypothesize that pembrolizumab in combination with Zepatier will help to reduce viral loads in those with untreated HCV..
- (2) **Objective:** To evaluate the response of HCV GT1 and GT4 to treatment as assessed by sustained virologic response at 4 and 12 weeks after the end of 12 to 16 weeks of pembrolizumab in combination with Zepatier dosing. Sustained virologic response is defined as HCV RNA below the LLOQ (either TD[u] or TND).
- (3) **Objective:** To evaluate the emergence of viral resistance-associated variants (RAVs) to pembrolizumab in combination with Zepatier in subjects with HCV GT1 or GT4 without RAVs as baseline ..
- (4) **Objective:** To evaluate the efficacy of pembrolizumab in combination with Zepatier as assessed by the proportion of subjects in the immediate treatment arm achieving

# Proprietary Information of MD Anderson

Protocol # 2016-0251

Date: February 24, 2020

118

undetectable (TND) HCV RNA and HCV RNA <LLOQ at Weeks 2, 4, 12 and Follow-Up Week 4 (SVR 4), Week 12 (SVR 12), and week 24 (SVR 24)..

## 8.13.2 Efficacy Analysis Populations

The ASaT population will serve as the primary population for the analysis of HCV efficacy data in this study. A supportive analysis using the Per- protocol (PP) population will be performed for the primary (SVR12) and key secondary efficacy endpoints. The PP population is a subset of the ASaT population. The PP population excludes subjects due to important deviations from the protocol that may substantially affect the results of the primary and key secondary efficacy endpoints. Potential violations that may result in the exclusion of a subject from the PP population include:

- Violations of specific inclusion/exclusion criteria:
  - The subject is infected with HCV of genotype other than GT1 or GT4, at entry or during the course of the study, including a mixed GT infection (with a non-GT1 or GT4) or non-typeable genotype.
  - The subject received concomitant medications that are prohibited due to their potential to result in a clinically significant lowering of Zepatier concentration (see Section 5.5.2 for specific details of prohibited medications). Further, any co-administered medication, currently unidentified, but for which subsequent clinical drug-drug interaction data indicate that co-administration with Zepatier leads to a clinically significant lowering of Zepatier concentrations.

Other violations may be identified during the course of data collection and they will be listed specifically in the clinical study report (CSR).

A subject with important deviations from the protocol as described above at randomization will be excluded from the PP population. For subjects with important deviations from the protocol as described above during course of the treatment, data obtained subsequent to the violation will be excluded from analysis.

Subjects will be included in the treatment group to which they are randomized for the analysis of efficacy data using both the ASaT and PP populations. Details on the approach to handling missing data are provided in Section 8.13.3.

## 8.13.3 Statistical Methods for Efficacy Analyses

### Missing values

A missing data point for a given study visit may be due to any one of the following reasons: a visit occurred but data were not collected or were unusable; a visit did not occur; or a subject discontinued from the study before reaching the visit. Subjects who prematurely discontinued the assigned treatment are encouraged to remain in the study for the follow-up, if possible.

# Proprietary Information of MD Anderson

Protocol # 2016-0251

Date: February 24, 2020

119

The HCV RNA outcome is categorized as TND, TD(u), and TD(q). There are 3 types of missing data handled by different approaches.

1. Intermittent missing: If a missing data point is immediately preceded and followed by non-missing HCV RNA outcomes, the missing value would be imputed to the worse outcome of the two. For example, if a missing data point is preceded by TD(q) and followed by TD(u) or TND, then the missing value would be imputed as TD(q); if a missing data point is preceded by TD(u) and followed by TND, then the missing value would be imputed as TD(u); when a missing value is flanked by two TND, then the missing value would be imputed as TND.
2. Non-intermittent missing related to the study drug: For missing values due to premature study discontinuations due to treatment related reasons either for safety or efficacy, the missing values will be considered as treatment failures.
3. Non-intermittent missing unrelated to the study drug: For missing data due to premature study discontinuations with reasons unrelated to treatment such as loss to follow-up, protocol violation, withdrawal of consent, administrative reasons, etc., the missingness mechanism is unlikely to be related to subjects' response to the HCV treatment, and therefore the missing at random (MAR) assumption is reasonable. The approaches to address this type of missing data depend on the analytical strategy, and they are described in the following sections.

In addition, a missing baseline/Day1 HCV RNA result will be replaced with a screening result, if available.

Approaches to handle non-intermittent missing values due to prematurely discontinuing from the study:

- Treatment-Related Discontinuation = Failure (TRD=F) approach: The treatment related type 2 missing will be considered as failure; whereas the subjects who have the type 3 missing value and do not have virologic failure during the observed study period will be excluded from the analysis for the time points following their study withdrawal. Note that subjects with documented virologic failure during the treatment or follow-up period, even if they withdrew prematurely due to reasons not related to study drug, are classified as failures.
- Missing = Failure (M=F) approach: Any non-intermittent missing (i.e., the type 2 and 3 missing) will be imputed as failure, regardless of the reason for study discontinuation.

## 8.13.4 Subgroup Analyses and Effects of Baseline Factors

To assess the consistency of the response across various subgroups, the SVR12 rate with 95% CIs will be estimated within each category of the following classification variables:

- Sex (female, male)

# Proprietary Information of MD Anderson

Protocol # 2016-0251

Date: February 24, 2020

120

- GT (1a, 1 non-a, 4)
- Stage of fibrosis (Non-cirrhotic vs. Cirrhotic)
- *IL28B* CC genotype vs. non-CC genotype
- HCV RNA at baseline, low ( $\leq 800,000$  IU/mL) versus high ( $> 800,000$  IU/mL)
- IFN treatment eligibility status (eligible or ineligible)

## 8.13.5 Subject Virologic Failure: Non-response, Rebound, Breakthrough, and Relapse

Summary statistics will be provided to describe the rates of occurrence of subject virologic non-response, rebound, breakthrough, and relapse. Definitions for subject virologic onresponse, rebound, breakthrough, and relapse are in Section 4.2.4.3.1.2. Viral resistance testing will focus on the entire NS3/4A and NS5A regions for all subjects and for those who meet the subject virologic failure criteria.

## 8.13.6 Compliance (Medical Adherence)

In this study, as part of the routine recording of the amount of study treatment taken by each subject, the number of tablets remaining in study packaging will be counted, reviewed, and recorded at regular intervals. These results will be used to calculate subject compliance. A day within the study will be considered an “On-Therapy” day if the subject takes the Zepatier. The “Number of Days Should be on Therapy” is the total number of days from randomization to the date of the last dose of study medication for that subject. Note, the date of the last dose of study medication would be the last scheduled day for treatment administration for subject who completed the assigned treatment.

